## 6.6. Interim Analyses and Data Monitoring

Refer to Section 6.6 of the master SAP for details of interim analyses. The details of the futility analysis are provided below. If enrollment is nearing completion at the timepoint of interim futility analysis (study enrollment projected to be completed within weeks), the below futility analysis will not be completed.

A futility analysis will take place after approximately 280 subjects eligible for the primary analysis subgroup have been enrolled and randomized. If protocol version 6.0 is implemented after the 280th subject is randomized, then the futility analysis will be based on data observed by the implementation date. Subjects discharged to locations other than LTAC, Hospice care or other hospital, and with no other follow-up data

indicating death or mechanical ventilation will be treated as non-events and censored at Day 29 for futility analysis. Subjects that are lost to follow-up or terminated early before Day 29 prior mechanical ventilation or death but were hospitalized at their last assessment will be considered non-events and censored at the date of their last observed assessment. Subjects that are lost to follow-up or terminated early after discharge or after Day 29 prior mechanical ventilation or death will be considered non-events and censored at Day 29. Subjects who complete follow-up without mechanical ventilation or death will be considered non-events and censored at Day 29. Mechanical ventilation or death that occur after Day 29 are considered non-events and censored at Day 29. No other imputation methods will be applied for the futility analysis.

For the futility analysis, the conditional power (the probability of rejecting the hypothesis that the proportion who survive without mechanical ventilation is the same between subjects who received active treatment versus those subjects who received placebo given the data observed) will be computed for the randomized subjects eligible for the primary analysis subgroup. The conditional power will be computed under the hypothesized treatment effect (a relative risk of 2.2). If the conditional power under the hypothesized treatment effect is less than 20%, the DSMB could recommend stopping the study for futility.

To consider all accumulated data properly, the interim Z value for the conditional power calculation will be based on a test of difference in the Kaplan-Meier (KM) estimates at Day 29, as some subjects will be in the middle of their follow-up. The alpha used in the conditional power calculation will be 0.049 to account for the spending of alpha= 0.001 during the first interim analysis. The hypothesized drift parameter will be updated by the lumped event rate and will be based on the overall interim event rate and the assumed relative risk rather than the interim relative risk. The unconditional power will be updated for a z-test (unpooled variance) of the difference in KM estimates using the current overall event rate and the hypothesized relative risk of 2.2. Based on these assumptions the following formula will be used to calculate conditional power (CP):

$$CP = \frac{t\hat{\theta}_t + \theta_F(1-t) - Z_{1-\alpha/2}}{\sqrt{1-t}}$$

where  $\hat{\theta}_t$  is the estimated drift parameter at information time t.  $\hat{\theta}_t$  can be estimated using

$$\hat{\theta}_t = \frac{B_t}{t}, B_t = Z_t \sqrt{t}$$

where  $Z_t$  is the interim Z statistic of difference in KM estimates using an unpooled variance estimate.  $\theta_F$  is the drift parameter at the final time and can be estimated as

$$\theta_F = Z_{1-\alpha/2} + Z_{1-\beta}$$

where Z is the standard normal with  $\alpha=0.49$  and  $1-\beta$  is the recalculated unconditional power using the pooled event rate,  $\bar{p} = \frac{\hat{p}_1 + \hat{p}_2}{2}$ , at information time, t and  $\hat{p}_1$  and  $\hat{p}_2$  are the KM estimates of each group. The updated conditional power can be estimated as

$$1 - \beta = \Phi\left(z - Z_{1-\frac{\alpha}{2}}\right) + \Phi\left(-z - Z_{1-\frac{\alpha}{2}}\right), z = \frac{p_A - p_B}{\sqrt{\frac{p_A(1-p_A)}{n_A} + \frac{p_B(1-p_B)}{n_B}}}$$

where  $\Phi$  is the standard normal distribution function and  $p_A$  and  $p_B$  are the group proportions that are consistent with a relative risk of 2.2 and  $\bar{p}$  at information t.  $p_A$  and  $p_B$  can be calculated as

$$p_B = \frac{2\bar{p}}{3.2}, p_A = 2.2p_B$$

Finally, information time, t, can be estimated as

$$t = \frac{E}{400\bar{p}}$$

where E is the total number of events at the time of the futility analysis.

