#### **6.5.1.3. Imputation Strategy for Subjects Lost to Follow-up while Hospitalized or Transferred**

This group includes subjects with post-baseline data available who were lost to follow-up or terminated early from the study prior to Day 29 and prior to death or progression to mechanical ventilation and were still hospitalized or discharged to LTAC, hospice care or other hospital at the time of their last assessment. Missing incidence of mechanical ventilation or death data for these subjects will be imputed using the algorithm described below that takes into account each subject's baseline covariates and time of last assessment. For each of these subjects with missing event, the first step will be to estimate the probability of having an event between their last assessment date and Day 29 which will be estimated from a Cox model as described below:

**Step 1:** Define a dataset including all subjects regardless of missingness except those that have no post baseline data. For all subjects who terminated early without event, consider them as non-events and censor them at the time of last assessment.

**Step 2:** Fit a Cox proportional hazards model for all subjects in step 1 using the following covariates: randomized treatment group (trtvar), baseline dexamethasone use (basedexavar), baseline actual ordinal score (baseordscorevar), age, indicator for black or Hispanic ethnicity (blackhispfl), presence of 2 or more comorbidities(comorb2fl), and baseline CRP (basecrp). The resulting Cox proportional hazards model will be of this form:

$$h(t) = h_0(t) \exp(b_1X_1 + b_2X_2 + \dots + b_pX_p)$$

where

$h(t)$ : Expected hazard at time t.

$h_0(t)$ : Baseline hazard function and represent the hazard when all the covariates are zero.

$X_1, X_2, \dots, X_p$  : Covariates in the cox model

$b_1, b_2, \dots, b_p$  : Model coefficients.

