## Appendix 6 BET-B

Endpoint	Analysis	Imputation/Censoring Method
mg/L.	Sensitivity	
 
Use the complete data for ordinal score to define survival without respiratory failure.
 
Subjects whose last assessment in the study is before Day 29 and were discharged to a location other than LTAC, hospice care or other hospital, or progressed to mechanical ventilation or death after Day 29 will be considered non-events and censored at Day 29.
 
Subjects whose last assessment in the study is before Day 29 and before progression to mechanical ventilation or death and without being discharged to a location other than LTAC, hospice care or other hospital at their last assessment will be considered non-events and censored at the date of their last observed assessment.
 
Subjects who complete follow-up without mechanical ventilation or death will be censored at the expected study Day 29.
 

Time to Sustained Recovery up to Day 60 in subjects who are < 85 years old, have baseline clinical status of 5 or 6, and baseline CRP < 150 mg/L.	Primary and subgroup	
 
Use the complete data for ordinal score to derive sustained recovery.
 
Subjects whose last assessment in the study is prior to Day 60 prior to recovery will be considered not recovered and censored at the date of last follow-up.
 
Death prior to recovery will be considered not recovered and censored at expected study Day 60.
 

	Sensitivity	
 
Use the complete data for ordinal score to derive sustained recovery.
 
Subjects whose last assessment in the study is prior to Day 60 after discharge from the hospital to a location other than LTAC, hospice care or other hospital will be treated as recovered by Day 60. Their time to recovery will be the day the time of their first observed/imputed recovery score (i.e; 1, 2, 3) or the day of discharge, whichever comes first.
 
Subjects whose last assessment in the study is prior to Day 60 without being discharged from the hospital to a location other than LTAC, Hospice care or other hospital at their last assessment will be considered not recovered and censored at the date of last follow-up.
 
Death prior to recovery will be considered not recovered and censored at expected study Day 60.
 

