### 8.2.1. Time to Mechanical Ventilation or Death Up to and Including Day 29 for Primary Endpoint Subgroup and All Subjects in ITT Population

The time to mechanical ventilation or death up to and including Day 29 will be defined as the elapsed time (in days) from Study Day 1 to date of invasive mechanical ventilation/ECMO or death. For the primary analysis of this endpoint, all subjects lost to follow-up or terminated early prior to death or progression to invasive mechanical ventilation will be considered non-events and censored at the date of their last observed assessment. As sensitivity analysis of this endpoint, any subjects that are lost to follow-up or terminated early prior to death or progression to mechanical ventilation and were discharged to a location other than LTAC, hospice care or other hospital, or progress to invasive mechanical ventilation/ECMO or death after Day 29 will be considered non-events and censored at Day 29 while subjects that are lost to follow-up or terminated early before Day 29 and before progression to invasive mechanical ventilation/ECMO or death and were either still hospitalized or discharged to LTAC, hospice care or other hospital at their last assessment will be considered non-events and censored at the date of their last observed assessment. If it is learned that a subject who terminated early had subsequently received ventilation or died prior to Day 29, then the subject will be classified as having the event. Subjects who complete follow-up without an event will be censored at the date of their expected Study Day 29 visit. Events that occur after Day 29 will be censored at the expected Study Day 29 date.

Table 7 will present median time to event along with corresponding 95% confidence intervals for each Lenzilumab + RDV long with the hazard ratio estimate and p-value from a Cox proportional hazards model for subjects in the primary subgroup. Restricted mean survival time estimates (RMST) which do not rely on the proportionality assumption will be provided for each treatment group and actual baseline ordinal score stratum as well as the difference in restricted mean recovery time between treatment groups within each of the

baseline ordinal score strata for the primary subgroup ([Table 9](#)). For both the Cox proportional hazards model and the RMST method, tied event times will be handled using the Efron method.

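### The futility rules in SAP 6.6 put inconsistent destination limits on subjects lost after discharge, so read literally a loss after LTAC or hospice discharge counts as event-free to Day 29

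*SAP*

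**What the plan says.** SAP 6.6 (Interim Analyses and Data Monitoring) sets the outcome coding for the futility look in consecutive sentences.

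- **Rule 1.** "Subjects discharged to locations other than LTAC, Hospice care or other hospital, and with no other follow-up data" of death or ventilation are non-events censored at Day 29.
- **Rule 2.** Subjects lost before Day 29 without an event "but were hospitalized at their last assessment will be considered non-events and censored at the date of their last observed assessment".
- **Rule 3.** "Subjects that are lost to follow-up or terminated early after discharge or after Day 29 prior mechanical ventilation or death will be considered non-events", and are censored at Day 29.

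The paragraph closes the list: "No other imputation methods will be applied for the futility analysis".

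Three other places sort early losses by discharge destination:

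- SAP 6.5.1.3, imputation for the primary endpoint, forms one group of subjects who "were still hospitalized or discharged to LTAC, hospice care or other hospital at the time of their last assessment".
- SAP 8.2.1, sensitivity analysis of time to ventilation or death: subjects who "were either still hospitalized or discharged to LTAC, hospice care or other hospital at their last assessment will be considered non-events and censored" at the last observed assessment.
- SAP Table 2, sensitivity row for the same endpoint, does likewise for those "without being discharged to a location other than LTAC, hospice care or other hospital at their last assessment will be considered non-events and censored" at that date.

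**The concern.** Rule 1 withholds the event-free credit from subjects sent to LTAC, hospice or another hospital. Rule 3 gives it back once they are lost, because it speaks of discharge without a destination. Rule 2, where the rest of the SAP would place them, names only the hospitalised. Two programmers could code these subjects differently, and each could cite 6.6.

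These are plausibly among the higher-risk losses, and carrying them to Day 29 as non-events keeps them in the risk set with no chance of an event. The Day 29 Kaplan-Meier estimates determine the interim Z, the pooled event rate and the information time. Together these give the conditional power that the DSMB compares with 20%. The coding should be settled before anyone sees on which side of 20% the result falls.

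**Working it through.** **1. The rules side by side.**

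| Lost, no event seen, last known to be | Rule 1 | Rule 2 | Rule 3 | Literal result |
|---|---|---|---|---|
| Discharged, not to the three destinations | met | not met | met | non-event to Day 29 |
| Still in hospital | not met | met | not met | censored at last assessment |
| Discharged to LTAC or hospice | not met | not named | met | non-event to Day 29 |
| Moved to another hospital | not met | can be met | met | two answers |

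The last two rows are the problem.

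**2. The plan's own power figure.** SAP section 5: 400 in the subgroup, odds ratio 2.5, two-sided alpha 0.049 (critical value 1.969).
- Control 16%: odds 0.16/0.84 = 0.1905; divided by 2.5 = 0.0762; treated rate 7.08%. z = 0.0892/√(0.16×0.84/200 + 0.0708×0.9292/200) = 2.82; power = Φ(2.82 − 1.969) = 80.3%.
- Control 21%: treated rate 9.61%; power 89.2%.

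Pooled variance gives 79.7% and 88.7%. The stated 80% and 89% reproduce. No figure is in dispute; this only confirms the set-up.

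**3. Conditional power under the two codings.**

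From the SAP: about 280 subjects at the look, 1:1 allocation, so 140 per arm; 400 at the end; alpha 0.049; relative risk 2.2; threshold 20%; the 6.6 formulas. The normal distribution function Φ is applied to the conditional power expression, and alpha is 0.049 throughout.

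Assumed: 22 placebo and 18 lenzilumab events, half before Day 10; three subjects per arm lost at Day 10 after discharge to one of the three destinations; everyone else followed to Day 29 or an event.

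*Coding A, Rule 3 as written (non-event to Day 29).*
- Event rates: 22/140 = 15.71%; 18/140 = 12.86%.
- Z = 0.02857/√(0.1571×0.8429/140 + 0.1286×0.8714/140) = 0.02857/0.04179 = 0.684.
- Pooled rate 14.29%; t = 40/(400×0.1429) = 0.700.
- p_B = 2×0.1429/3.2 = 8.93%; p_A = 2.2×p_B = 19.64%; drift = 0.1071/√(0.1964×0.8036/200 + 0.0893×0.9107/200) = 3.098.
- Conditional power = Φ[(√0.700×0.684 + 3.098×0.300 − 1.969)/√0.300] = Φ(−0.853) = **19.7%**.

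*Coding B, censored at last assessment.*
- Placebo: 1 − (1 − 11/140)(1 − 11/126) = 15.90%. Lenzilumab: 1 − (1 − 9/140)(1 − 9/128) = 13.01%.
- Z (Greenwood variance) = 0.685; pooled rate 14.45%; t = 40/(400×0.14455) = 0.692; drift 3.120.
- Conditional power = Φ[(√0.692×0.685 + 3.120×0.308 − 1.969)/√0.308] = Φ(−0.788) = **21.5%**.

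With events spaced evenly over Days 2 to 28 instead, coding B gives 22.2%, hence about 22%.

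**4. Range over the assumed number of losses** (22 vs 18 events; coding A stays at 19.7%).

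| Lost at Day 10 | Coding B |
|---|---|
| 3 / 7 / 14 per arm | 21.5% / 24.2% / 29.2% |
| 7 / 14, placebo only | 26.6% / 34.8% |
| 7 / 14, lenzilumab only | 17.7% / 15.8% |

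**5. Away from the threshold** (0 to 14 lost, in either or both arms).
- 22 vs 10 events: 91.5% under A; 87.8% to 94.9% under B.
- 22 vs 22 events: 3.6% under A; 2.9% to 10.2% under B.

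In a mid-range case, 20 vs 13 events, coding A gives 46%. Balanced losses of one to five per arm move it to about 47% to 51%. Five losses in one arm only move it to 52% to 55% (placebo) or 43% (lenzilumab). No decision changes in any of these.

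**The case against.** **Discharge may be shorthand.** SAP 6.5.1.2 is headed as covering losses while discharged, and defines them as discharges outside the three destinations. SAP 6.5 and 6.5.2 use the word in a similar way. Read so, Rule 3 agrees with Rule 1. This has force, but the usage is not consistent: Step 4 of 6.5.1.3 describes its own group, the hospitalised or transferred, as lost while discharged or transferred. On this reading losses after LTAC or hospice discharge also have no rule at all, because Rule 2 omits them and no other method is allowed. The text still needs repair.

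**Rule 1 may be for subjects still in follow-up and Rule 3 for those lost.** Rule 1 contains no such limit. This reading would also credit lost LTAC and hospice subjects to Day 29, and it leaves the overlap for another hospital.

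**Rule 1 is silent about the three destinations, so nothing strictly contradicts.** This stands for LTAC and hospice, where the literal text gives one answer, though not the grouping used elsewhere. Only for a move to another hospital does it give two.

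**A reader might infer that the interim and final analyses treat these subjects in opposite ways.** The documents do not support this. The methods differ by design even for ordinary discharges, which are non-events at the look and multiply imputed at the end. Nor is the cited grouping the main rule of 8.2.1: its primary analysis censors every early loss at last assessment, and the grouping belongs to its sensitivity analysis.

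**The impact is assumed.** This stands. SAP section 5 expects little missing data, and these losses are a subset of it.

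**Conclusion.** The destination limits in SAP 6.6 are inconsistent and should be reconciled. Read literally, the plan credits losses after LTAC or hospice discharge as event-free to Day 29 and leaves losses after a move to another hospital with two possible codings.

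The size is modest. Few or balanced losses barely move Z: 0.684 against 0.685 with three per arm. The change in conditional power then comes mainly from the lower information time. It can alter the recommendation only when conditional power is already near 20%, as in the example of 19.7% against about 22%. The direction depends on which arm has the losses. All of this rests on assumed counts and timings.

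A reader might infer that the trial's conclusion is at risk. It is not: the final analysis has its own missing-data rules, the DSMB is not bound by the 20% criterion, and the look is skipped if enrolment is nearly complete. Nor should the gap be sized by supposing that a lost subject later had an unseen event, since censoring at last assessment would not capture that event either.

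**What to change.** Change two phrases in SAP 6.6 before the futility analysis is run.

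- **Rule 3:** limit the discharge phrase to read *after discharge to a location other than LTAC, hospice care or other hospital*.
- **Rule 2:** widen the hospitalised phrase to read *hospitalized or discharged to LTAC, hospice care or other hospital at their last assessment*.

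All three destinations are then censored at last assessment. This matches the grouping in 6.5.1.3 and the censoring in the 8.2.1 sensitivity analysis. It aligns the grouping, not the method: the final primary analysis will still impute these outcomes.

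The cost is a wording change and the matching line in the interim program. No data collection, design feature or clinical rule changes.

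### SAP 6.6 prints conditional power as a normal deviate without Φ, and alpha as 0.49 instead of 0.049; taken literally, the missing Φ alone flags any true conditional power below 58%

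*SAP*

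**What the plan says.** SAP section 6.6 defines conditional power as "the probability of rejecting the hypothesis that the proportion who survive without mechanical ventilation is the same" in the two arms, given the data so far. It attaches the decision rule to that quantity: "If the conditional power under the hypothesized treatment effect is less than 20%, the DSMB could recommend stopping the study for futility".

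It then announces: "Based on these assumptions the following formula will be used to calculate conditional power (CP"). What follows is "CP = \frac{t\hat{\theta}_t + \theta_F(1-t) - Z_{1-\alpha/2}}{\sqrt{1-t" and the closing brackets: a numerator divided by √(1−t), with no Φ in front.

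On alpha, the section first says: "The alpha used in the conditional power calculation will be 0.049 to account for the spending of alpha= 0.001". A few lines later, where the final drift θ_F is defined as a sum of two normal quantiles, it says: "where Z is the standard normal with $\alpha=0.49".

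Finally, the power term 1−β inside θ_F is first described as recalculated unconditional power. Its formula, which does use Φ, is then introduced with "The updated conditional power can be estimated as".

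Protocol section 9.2.3 has the same 20% rule and leaves the details to the SAP, so SAP 6.6 is the operative specification.

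**The concern.** A probability lies between 0 and 1; the printed expression does not. It is the argument to which Φ should be applied. The prose (a probability, 20%, alpha 0.049) and the formula that the SAP says to use therefore conflict, and nothing elsewhere in the SAP or protocol corrects the formula. The label on 1−β adds to the confusion: two formulas in the section carry the name conditional power, and the one containing Φ is not conditional power.

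At stake is the futility report to the DSMB in a trial meant as a confirmatory test of the LIVE-AIR result. If the section is programmed as printed, a trial more likely than not to succeed could be reported as below the futility threshold.

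**Working it through.** **Inputs from the documents.** Final subgroup size 400 and two-sided alpha 0.049 (SAP 5; alpha also in SAP 6.8 and 8 and protocol 9.2.1). Relative risk 2.2, threshold 20%, futility look at about 280 subgroup subjects (SAP 6.6). Equal planned arms (SAP 4.3), taken as 200 per arm in the subgroup.

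**The plan's own power.** With odds ratio 2.5, a control rate of 16% gives a treated rate of 7.08%. The unpooled z is (0.16 − 0.0708)/√[(0.16×0.84 + 0.0708×0.9292)/200] = 2.820, and power is Φ(2.820 − 1.969) = 80.3%. A control rate of 21% (treated 9.61%) gives 89.2%. A pooled test gives 79.7% and 88.7%. The stated 80% and 89% are reproduced.

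**Result that needs no further assumption.** Let x be the printed ratio, so that true conditional power is Φ(x). The intended rule Φ(x) < 0.20 means x < −0.842. The literal rule x < 0.20 means Φ(x) < Φ(0.20) = 57.9%. So 57.9% is the upper edge of what the literal rule flags, and it does not depend on t, the event rate or the effect.

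**Illustration.** The SAP does not fix the following, so they are assumed: t = 0.7 (t is event-based; 280/400 = 0.7), pooled rate (16% + 7.08%)/2 = 11.54%, and positive Z favouring lenzilumab.

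- Rates from the SAP's formulas: p_B = 2×0.1154/3.2 = 0.0721 and p_A = 2.2×0.0721 = 0.1587.
- z = (0.1587 − 0.0721)/√[(0.1587×0.8413 + 0.0721×0.9279)/200] = 2.734.
- Unconditional power at 0.049: Φ(2.734 − 1.969) = 0.778.
- θ_F = 1.969 + 0.766 = 2.734.
- Printed ratio at interim Z: x = (√0.7·Z + 0.3×2.734 − 1.969)/√0.3.

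At Z = 0, x is −2.10. At the Z expected under the design effect (2.734×√0.7 = 2.29), x is 1.40. It exceeds 1 once Z passes 2.03, and lies between 0 and 1 only for Z from about 1.37 to 2.03.

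The flag boundary is Z* = [c√0.3 − 0.3θ_F + z_crit]/√0.7, with c = −0.842 if Φ is applied and c = 0.20 if not:

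- Intended: (−0.461 − 0.820 + 1.969)/0.837 = 0.82.
- Φ missing: (0.110 − 0.820 + 1.969)/0.837 = 1.50.

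The chance of a flag under the design effect is Φ(Z* − 2.287): Φ(−1.465) = 7% against Φ(−0.784) = 22%.

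**Adding alpha = 0.49.** The quantile is 1.969 at 0.049 and 0.690 at 0.49. If 0.49 is used in θ_F only, θ_F = 0.690 + 0.766 = 1.456. If it is also used in 1−β, power becomes 0.980 and θ_F = 0.690 + 2.050 = 2.740, so the error almost cancels.

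| Reading | Flag if Z below | True conditional power at boundary | Chance of flag under design effect |
|---|---|---|---|
| Intended | 0.82 | 20% | 7% |
| Φ missing, 0.049 throughout | 1.50 | 58% | 22% |
| Φ missing, 0.49 in θ_F only | 1.96 | 82% | 37% |
| Φ missing, 0.49 in θ_F and 1−β | 1.50 | 58% | 22% |
| Φ restored, 0.49 in θ_F only | 1.28 | 44% | 16% |
| Φ restored, 0.49 in θ_F and 1−β | 0.82 | 20% | 7% |
| Φ restored, 0.49 also as critical value | −0.71 | 0.1% | 0.1% |

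The last row contradicts the stated 0.049 and is shown only for completeness.

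**Sensitivity, intended against Φ missing only (chance of a flag under the design effect).**

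- Pooled rate 15%, roughly the 21% control scenario (θ_F = 3.190): 2% against 9%.
- t = 0.6: Z below 0.44 against 1.29; 5% against 20%.
- t = 0.8: Z below 1.17 against 1.69; 10% against 22%.
- A 220/180 split in either direction: 7–8% against 21–24%.

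**The case against.** The best case against is that the intent is not in doubt. Conditional power is defined in words as a probability, the threshold is a percentage, and 0.049 appears everywhere else, so only one correction fits. A programmer who obtained −2.10 or 1.40 would see that something was missing. The rule is non-binding, the look is dropped if enrolment is almost finished, and a futility look does not inflate type I error. If 0.49 is carried consistently through θ_F and 1−β it nearly cancels, and the larger effects need one symbol to take two values. A symbol or digit lost when the PDF was converted to text cannot be wholly excluded.

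Much of this stands, and it limits the consequence. The intended rule also flags some favourable trends (Z from 0 to 0.82); the error widens that region rather than creating it. Two points remain. First, the output does not always give itself away: for Z between about 1.37 and 2.03 the printed ratio looks like an ordinary probability, and the literal boundary of 1.50 lies in that interval. With Φ restored, a wrong alpha gives no warning at all. Second, Φ is intact in the neighbouring power formula, which makes a conversion loss there unlikely. A glance at the source PDF would settle both symbols.

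**Conclusion.** The concern holds. As written, the futility calculation in SAP 6.6 is not a probability and cannot properly be compared with 20%; the literal comparison flags every true conditional power below 57.9%. That figure rests on no assumption beyond reading the formula as printed. The rise in the chance of a flag from 7% to 22% when the design effect is true rests on t = 0.7, 200 per arm and a pooled rate of 11.5%. Over the alternatives tried, the literal rule's chance was roughly two to four times the intended one.

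The alpha misprint is a separate error whose effect depends on where it is used, from negligible to a boundary at 44% true conditional power with Φ restored. Neither error touches the final test. This should be fixed, because the section defines a decision quantity for the DSMB, but it is a correction of specification and not a flaw in the design.

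**What to change.** In SAP 6.6:

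- Write CP = Φ{[t·θ̂_t + θ_F(1−t) − Z_(1−α/2)]/√(1−t)}.
- Change 0.49 to 0.049, and state that it applies to the critical value, θ_F and 1−β alike.
- Call 1−β the updated unconditional power.

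It would also help, though it is optional, to say that n_A and n_B are the projected final subgroup arm sizes and that positive Z_t favours lenzilumab. The cost is SAP wording only. If the futility program has already been written, check it against the corrected formula.
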